### **5.3 PATIENT WITHDRAWAL FROM THE TRIAL**

#### **Reasons for Mandatory Trial Discontinuation**

If a female patient becomes pregnant, she must stop taking study medication and must be withdrawn from the trial. The patient must be followed by the investigator through pregnancy outcome. The mother (and infant) will be followed as considered appropriate by the investigator and study physician ([name] or designee). For reporting purposes pregnancy is not considered a serious adverse event (SAE).

#### **Other Reasons for Trial or Treatment Discontinuation**

The following events are considered appropriate reasons for a patient to discontinue from the trial:

- The patient withdraws consent or requests to be withdrawn from the trial. It is fully understood that all patients volunteer for the trial and that they may withdraw their consent to continue trial participation at any time.
- The patient experiences an adverse event (such as AE grade 3) that in the opinion of the investigator or Safety Monitor is caused by or exacerbated by any of the trial procedures or study medication, of sufficient intensity to warrant discontinuation.
- The patient refuses to comply with the requirements for trial participation.
- Investigator's decision.

When possible, the investigator should discuss the potential discontinuation of a patient with the study physician ([name] or designee) in advance.

#### **Patient Discontinuation Notification**

The investigator must notify the study designated physician ([name] or his designee) as soon as possible if any patient prematurely discontinues from the trial. The date when the patient is withdrawn and the primary reason(s) for discontinuation must be recorded in the CRF; additional information may be requested to complete a discontinuation narrative. Patients will be considered "lost to follow up" only after reasonable, documented attempts to reach the patient prove unsuccessful. In all cases, a reasonable effort must be made to

determine the reason(s) that a patient fails to return for required trial visits or discontinues from the trial. If a patient is withdrawn from the trial early during the treatment phase (regardless of the cause), all of the Day 28 evaluations should be performed at the time of withdrawal, to the extent possible.

## **6. INVESTIGATIONAL PRODUCT (IP)**

### **5.1 DESCRIPTION OF IP**

For the purpose of this protocol, the term ‘investigational product (IP)’ is interchangeable with the term ‘study medication’.

### **5.2 Study Medication**

OCA is a white, round tablet with “INT” engraved on one side and “3547” engraved on the other side. All study medication will be provided as a tablet for oral administration and provided in high density polyethylene (HDPE) bottles with an induction seal and child proof caps.

All study medication (OCA and matching placebo) will be provided by Intercept Pharmaceutical and manufactured according to Good Manufacturing Practice (GMP).

### **6.3 PACKAGING, LABELLING, AND STORAGE**

The packaging and labeling of study medication supplies will be performed according to GMP standards by a designated qualified vendor and in accordance to 21 CFR 312.6. It will be Limited by Federal Law to Investigational Use Only.

The designated drug packaging/distribution vendor will also be responsible for the distribution of the study medication to the investigator and, where applicable, providing the Qualified Person (QP) release of study medication. Study medication should be stored in the containers in which they are received from the Sponsor’s supplier, at controlled room temperature, and protected from excess humidity.

Study medication will be packaged for the trial as described below. Study medication for the trial will be packaged and labeled as single bottles containing 30 tablets and should be dispensed to the patient as received. The investigative pharmacist at the site will prepare the study medication for appropriate dispensing to the subjects according to standard operating procedures.

### **6.4 DOSE AND ADMINISTRATION**

Heavy drinker subjects will be randomized to placebo or OCA (10 mg). Study medication will be administered orally, once daily for 28 days during the study. Patients will be instructed to begin dosing on the day after the Day 0 visit and after the baseline endpoint measurements are obtained (i.e., on Day 1) and to take study medication with water, approximately 30 minutes prior to breakfast. Patients must be instructed to swallow the tablet whole; they must not chew, divide, or crush the tablet.

### **Missed Doses**

Patients who miss a dose of study medication should be instructed to take it later the same day, as soon as they remember. ‘Missed’ doses should not be taken on a subsequent day (i.e., the patient should not take more than the prescribed daily dose)

## **Overdosage**

The maximum dose of OCA that has been given to humans is 500 mg as a single dose and 250 mg as a multiple dose. Reversible increases in aminotransferases were seen in most of the healthy volunteers who took 250 mg OCA. There is no specific information available regarding the treatment of possible overdose with OCA. If overdose occurs in a patient enrolled in the trial, general medical supportive measures should be provided, including observation and follow up (e.g., serum chemistry) as appropriate. Due to the extensive enterohepatic recirculation of the drug it is likely that it will take several days before blood (and organ) concentrations of the drug will decrease. Treatment with cholestyramine (Questran™), colestevam (Welcol™) and other bile acid sequestrants is both logical and recommended given that they should bind and eliminate the drug in feces. Although there is no experience with OCA, plasmapheresis might be expected to reduce circulating levels of the drug. The study physician ([name] or designee) should be notified immediately in the event of a significant overdose.

## **6.5 PRIOR AND CONCOMITANT MEDICATIONS OR PROCEDURES**

Relevant information about all concomitant drugs (including prescribed, over the counter, or herbal preparations) taken prior to and during the trial must be recorded in the source documents and CRF, as well as any dose or dose regimen changes that occur during the trial.

## **6.6 TREATMENT COMPLIANCE**

The investigator should assess the patient's compliance with dosing of study medication on an ongoing basis.

Patients should be instructed to retain all bottles of study medication, even if empty, and to return them to the investigator at the subsequent visit. The investigator or designee should perform drug accountability and, if applicable, follow up with the patient to retrieve any study medication bottles that have not been returned.

If the investigator has concerns about a patient's dosing compliance s/he should discuss this with the patient, assess the reasons for noncompliance and the likelihood that the patient will remain noncompliant, and notify the Sponsor accordingly. Continued trial eligibility should be assessed based on the patient's compliance with study medication dosing and clinic visits.

## **6.7 STUDY MEDICATION ACCOUNTABILITY AND RETENTION**

Intercept Pharmaceutical, Inc's representative will send study medication to the trial site under appropriate storage conditions. All shipments of study medication should be unpacked and the contents reviewed immediately upon receipt. If it is not possible to verify the contents immediately, they must be stored under the appropriate storage conditions until verification of the contents is possible (ideally, within 1 business day from receipt). The pharmacist or designee should verify the study medication against the shipment documentation. The pharmacist or designee should contact Intercept Pharmaceuticals immediately to report any concerns regarding the shipment.

All study medication will be provided for use only in this trial and is not to be used for any other purpose. The investigator or designee will maintain a full record of study medication accountability, including records of individual patient dispensing and final return or disposition (as directed by the Sponsor).

## **6.8 TRIAL OR SITE TERMINATION**

The Sponsor reserves the right to terminate the trial at any time. It is normal procedure to review the emerging clinical and safety data. As a result of such a review or a recommendation by the DSMB, it may be necessary to stop the trial before all patients have completed the trial.

The investigator must notify the Institutional Review Board/Independent Ethics Committee (IRB/IEC) of discontinuation of the trial and the reason for doing so.

## **7. TRIAL PROCEDURES**

### **7.1 SCREENING**

#### **Informed Consent**

The investigator or designee will explain the nature, purpose and risks of the trial to the patient and will provide him/her with a copy of the written information and informed consent form (ICF). The patient will be given sufficient time to consider the trial before deciding whether or not to participate. The patient will be informed that participation is voluntary and that her/his future medical treatment will not be compromised by participation in the trial and that s/he can withdraw from the trial at any time. The patient must be willing and able to provide written informed consent before entering the trial. The investigator or a medically qualified designee is responsible for administering and documenting the written informed consent of the patient.

#### **Screening Numbers**

At the Screening Visit, after the patient has provided written informed consent, the patient will be assigned a 5 digit subject participant (screening) number. This number will be recorded in the CRF.

#### **Patient Identification Assignment**

After the patient has met eligibility criteria and enrolls into the study, the patient will be assigned a unique 5 digit study ID number. This 5 digit number will be used to identify the participant throughout the trial and during the data analysis.

### **7.2 VISIT PROCEDURES**

Patients should be instructed to fast overnight (at least 8 hours) immediately prior to all at-clinic visits, including the Screening Visit. While fasting, water is permitted.

#### **Screening Procedures (≤30 days)**

The Screening Visit assessments must be performed within 30 days prior to Day 0 to determine whether the patient meets all the inclusion criteria and none of the exclusion criteria. Patients who do not fulfill all eligibility criteria will not be enrolled in the trial.

Screening Visit procedures are as follows:

- The patient is to review and sign the informed consent document. Informed consent must be obtained from the patient before performing any trial related procedures, including Screening procedures

- Collect medical and disease history
- Collect alcohol use history
- Verify inclusion and exclusion criteria for eligibility
- Perform a physical examination, including height (Screening only) and weight
- Record vital signs
- Perform a standard 12-lead electrocardiogram (ECG) –*Heavy Drinker Group Only*
- Record prior (within 30 days of screening visit) and current concomitant medications.
- Obtain blood samples for serum chemistry and hematology tests
- Obtain urine sample for dipstick urinalysis
- Perform a urine based beta human chorionic gonadotrophin ( $\beta$ -hCG) pregnancy test in females of childbearing potential

#### **Day 0 Procedures (Randomization and Baseline Study Day)**

- Review inclusion and exclusion criteria for eligibility
- Record vital signs
- Perform a Physical Examination
- Assess and record any pretreatment emergent events
- Record prior (within 30 days of Day 0) and current concomitant medications
- Assess Alcohol Consumption
- Perform an urine pregnancy test in females of childbearing potential
- Perform Hepatic CYP2E1 Measurement Study
- Perform Gut Permeability Test (Lactulose/ Mannitol test)
- Obtain safety labs (CMP, CBC and PT/INR)
- Obtain Research Blood samples as outlined in Table 1: Schedule of Study Procedures
- Obtain Stool Specimen (optional)
- Randomization to study drug (*Heavy drinker group only*)
- Dispense study drug (*Heavy drinker group only*) and instruct patient to begin dosing on the day after Day 0 visit and to take the study medication with water approximately 30 minutes prior to breakfast.

#### **Day 7 Procedures (+/- 2 days)- *Heavy Drinker Group Only***

- This consists of a telephone visit where the study staff will inquire with the subject on his/her wellbeing, compliance with study medication, adverse events and concomitant medication use.

### **Day 28 Procedures (+/- 2 days)**

Healthy non-drinkers controls will have repeated procedures at D0 performed. The same procedures will also be done in heavy drinkers when they complete the study drug for 28-day.

- Record vital signs
- Perform a Physical Examination
- Assess and record any Adverse Events
- Assess concomitant medications
- Perform a standard 12 Lead Electrocardiogram (*Heavy Drinker Group only*)
- Obtain Safety Labs (CBC, CMP and PT/ INR) (*Heavy Drinker group only*)
- Evaluation of Study Drug Compliance (*Heavy Drinker Group only*)
- Collection of all study medication and bottles (*Heavy Drinker Group only*)
- Assess Alcohol Consumption
- Perform Hepatic CYP2E1 Measurement Study
- Perform Gut Permeability Test (Lactulose/ Mannitol test)
- Obtain Research Blood samples as outlined in Table 1: Schedule of Study Procedures
- Obtain Stool Specimen (optional)
- Perform an urine pregnancy test in females of childbearing potential

### **Day 42 Follow-up Procedures (+/- 2 days) - *Heavy Drinker Group Only***

- Record vital signs
- Assess and record any Adverse Events
- Assess concomitant medications
- Obtain Safety Labs (CBC, CMP and PT/ INR)

### **Unscheduled Safety Visits**

The investigator may schedule an at-clinic Unscheduled/Safety Visit at any time if clinically warranted. Unscheduled and/or repeat assessments may be conducted. As appropriate, the Safety Monitor should be contacted.

## **7.3 PHYSICAL EXAMINATION AND VITAL SIGNS**

### **Physical Examination**

To assess for clinical findings, the investigator or designee will perform a physical examination at the time points specified in the Schedule of Trial Procedures (Tables 1). This includes height only at Screening.

### **Vital Signs**

The following vital signs will be assessed at indicated visits: body temperature, sitting heart rate, and sitting blood pressure (BP). When taking heart rate and BP readings, patients should be seated quietly for a minimum of 3 minutes before the reading is taken. The heart rate should be recorded over a 60 second period.

## **7.4 CLINICAL LABORATORY**

Blood samples for serum chemistry, hematology, and coagulopathy will be collected at every visit as detailed in the Schedule of Trial Procedures (Tables 1). The number and volume of samples to be collected at each visit will be detailed in the Standard Operating Procedures.

Full instructions concerning the number and type of samples to be collected at each visit, the required sample volumes, sample collection methods, sample processing, labeling, and shipping will be provided in a trial specific laboratory manual. All patients with laboratory tests containing clinically significant abnormal values should be followed regularly until the values return to normal ranges, until a valid reason for the AE (other than study medication related AE) is identified, or until further follow up is deemed medically unnecessary.

## **7.5 ELECTROCARDIOGRAM**

Standard 12-lead ECGs will be collected. The investigator or designee will review the 12-lead ECG and findings will be recorded in the CRF as normal, abnormal but not clinically significant, or abnormal and clinically significant. Any clinically significant abnormalities on ECGs recorded after Day 0 will also be documented as AEs and entered on the AE page of the CRF.

Investigative sites must retain a copy of all 12-lead ECGs evaluated by the investigator or designee. These ECGs must be clearly labeled with the subject's initials, Participant or Study ID Number, date and time.

The ECG read will be completed by the investigator or designee. At a minimum the following will be assessed: PR, QRS, QT and QTc intervals and a clinical evaluation for each ECG will be provided.

## **8. ADVERSE EVENTS**

### **7.1 DEFINITION AND REPORTING PERIOD FOR ADVERSE EVENTS**

Safety will be assessed in terms of AEs. All AEs, whether observed by the investigator, reported by the subject, noted from laboratory findings, or identified by other means, will be recorded from the time the patient signs the ICF until the patient completes trial participation.

AEs are defined as any untoward medical occurrence associated with the use of the study medication in humans, whether or not considered related to study medication. An AE (also referred to as an adverse experience) can be any unfavorable and unintended sign (e.g., an

abnormal laboratory finding), symptom, or disease temporally associated with any use of the study medication, without any judgment about causality and irrespective of route of administration, formulation, or dose, including an overdose. For this trial, study medication refers to OCA.

AEs include, but are not limited to: (1) a worsening or change in nature, severity, or frequency of condition(s) present at the start of the trial; (2) subject deterioration due to primary illness; (3) intercurrent illness; and (4) drug interaction.

Subjects should be questioned in a general way, without leading the patient or asking about the occurrence of any specific symptom. The investigator should attempt to establish a diagnosis of the event based on signs, symptoms, and/or other clinical information. The diagnosis and not the individual signs/symptoms should be documented as the AE. For example, if the underlying disease process is a stroke, it would not be appropriate to record the AE by describing the symptoms "sudden numbness, dizziness, and difficulty speaking." The AE medical term of "stroke or cerebrovascular accident" should be recorded as it more accurately describes the AE.

Following questioning and evaluation, all AEs, whether believed by the investigator to be related or unrelated to the study medication, must be documented in the subject's medical records, in accordance with the investigator's normal clinical practice and on the AE CRF. Each AE is to be evaluated for duration, intensity, frequency, seriousness, outcome, other actions taken, and relationship to the study medication.

#### *Pretreatment Event(s)*

Untoward events that occur between the time the patient signs the ICF for the trial and the time when that patient is first administered the study medication are classified as "pre-treatment" events. Any pretreatment event should be recorded as medical history.

## **7.2 Severity of AEs**

AEs must be graded for severity (i.e., intensity). A severity category of mild, moderate, or severe, as defined in Table 3, must be entered on the AE CRF. It should be noted that the term "severe" used to grade intensity is not synonymous with the term "serious." The assessment of severity is made regardless of study medication relationship or of the seriousness of the AE.

**Table 2      Severity of AEs**

Grade	Clinical Description of Severity
1 = Mild	Causing no limitation of usual activities; the subject may experience slight discomfort.
2 = Moderate	Causing some limitation of usual activities; the subject may experience annoying discomfort.
3 = Severe	Causing inability to carry out usual activities; the subject may experience intolerable discomfort or pain.

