#### **Adverse Events**

AEs will be coded using the Medical Dictionary of Regulatory Activities (MedDRA). Summary tables of treatment-emergent AEs will be provided. A TEAE is any AE that newly appeared, increased in frequency, or worsened in severity following initiation of study medication. The incidence of TEAEs will be tabulated by system organ class and preferred term for each treatment group, and by severity and relationship to treatment. Tables of TEAEs leading to study medication discontinuation and SAEs will be provided.

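### Table 2 grades every symptom-free laboratory adverse event as mild whatever its size, and section 9.3 plans no laboratory summary that would show the size

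*Combined protocol and SAP*

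**What the plan says.** Section 8, under the subheading numbered 7.1, brings laboratory results into the AE record: "All AEs, whether observed by the investigator, reported by the subject, noted from laboratory findings, or identified by other means, will be recorded", from consent to the end of participation. The same text makes AEs the basis on which safety is judged.

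The next subheading, 7.2, makes grading compulsory: "A severity category of mild, moderate, or severe, as defined in Table 3, must be entered on the AE CRF". The pointer is wrong. Severity is defined in Table 2, and Table 3 covers relationship to study medication. The three grades in Table 2 are:

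- Grade 1, mild: "Causing no limitation of usual activities; the subject may experience slight discomfort".
- Grade 2, moderate: "Causing some limitation of usual activities; the subject may experience annoying discomfort".
- Grade 3, severe: "Causing inability to carry out usual activities; the subject may experience intolerable discomfort or pain".

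Section 9.3 plans descriptive statistics for AEs. Treatment-emergent events are tabulated by MedDRA class and term, "for each treatment group, and by severity and relationship to treatment". Further tables cover SAEs and events that led to stopping study medication. Table 1 in section 3.2 schedules safety laboratory tests for heavy drinkers at Screening, Day 0, Day 28 and Day 42.

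**The concern.** Severity grade is the only measure of size in the planned safety analysis. For an abnormality that the participant does not feel, the definitions fix that measure in advance.

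Liver tests are where this matters most. The hepatic signals that the protocol itself cites are of a kind that laboratory tests pick up. Under Overdosage in section 6.4 it states: "Reversible increases in aminotransferases were seen in most of the healthy volunteers who took 250 mg OCA". Section 1.2 reports liver effects in rats and dogs. Neither predicts what will happen here: the volunteer dose is 250/10 = 25 times the trial dose, and the animal effects were confined to the top doses. They do show which signal the plan should be able to size.

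At stake is how the safety result reads. There are 15 participants per randomised arm. A severity table that lists every symptom-free laboratory event as mild looks reassuring, but it says nothing about whether the rises were small or large.

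**Working it through.** The protocol states no figure to reproduce. The check is a reading of the sections against each other, with one illustration.

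**Step 1. Is a laboratory abnormality an AE?** Yes. Section 8 (subheading 7.1) includes laboratory findings both in what is recorded and in its definition of an AE.

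**Step 2. Must it be graded?** Yes. Subheading 7.2 requires one of three categories on the CRF.

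**Step 3. Which grade fits an event with no symptoms?**

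| Grade | Effect on activities | Felt effect | Can a symptom-free laboratory AE meet it? |
|---|---|---|---|
| 1 | none | slight, possible | yes |
| 2 | some | annoying | no |
| 3 | unable | intolerable, or pain | no |

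The discomfort and pain element adds nothing for an event that is not felt. Only grade 1 is left, whatever the laboratory value.

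**Step 4. Does another section supply a laboratory criterion?** No. Sections 7.4 and 8.7 refer to clinically significant laboratory values, but for follow-up only. No multiple of normal, numerical grade or external toxicity scale appears anywhere.

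**Step 5. Does another planned analysis show size?** No. Section 9.3 covers AEs only. It has no change from baseline, shift table or listing for laboratory values.

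**Step 6. Illustration (hypothetical values).** Take a heavy drinker with ALT 60 U/L at Day 0 who reaches 600 U/L without symptoms. The 45 U/L limit is the one that section 5.2 uses for normal ALT and AST in controls.

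- Relative to Day 0: 600/60 = 10.
- Relative to the limit: 600/45 = 13.3.
- Grade under Table 2: 1, the same as for a trivial rise.

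**Step 7. Why baseline matters.** Heavy drinkers may enter with ALT and AST below 100 U/L, so a participant can start at just under 100/45 = 2.2 times the limit. A multiple of normal alone would mix entry level with change on treatment. Table 2 expresses neither.

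**Step 8. What the schedule allows.** Dosing starts on Day 1 and runs for 28 days (section 6.4), and Day 7 is a telephone contact. Scheduled post-baseline tests therefore fall at about the end of dosing and 42 − 28 = 14 days later. An earlier rise would be seen only at an unscheduled visit or at early-withdrawal testing. This limits any grading scale or summary equally.

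**The case against.** The strongest reply is that little in the protocol runs on the grade. A reader might infer three stronger conclusions, and the documents support none of them.

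- **That the safety tables would miss the event.** They would not. Section 9.3 counts it by preferred term, arm and relationship, and in the SAE or discontinuation tables where it qualifies. Only the severity breakdown loses its size.
- **That a grade 3 stopping trigger would fail.** Section 5.3 lists the case where "The patient experiences an adverse event (such as AE grade 3", but that is an example. The decision rests on the judgement of the investigator or Safety Monitor, and a separate item leaves discontinuation to the investigator alone. A symptom-free laboratory AE cannot match the example, yet it can still lead to discontinuation.
- **That the DSMB would be misled.** The DSMB text in section 9 says that it reviews safety data under a charter that is not included here. Nothing restricts it to AE grades.

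Other routes are also independent of grade. Section 8.4 allows SAE status for an important medical event, subheading 7.2 separates severity from seriousness, and sections 7.4 and 8.7 require follow-up of clinically significant laboratory values.

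All of this stands, and it protects individual participants. It does not supply the missing magnitude in the reported comparison of OCA with placebo.

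A second reply is that laboratory summaries alone would show the size without regrading, and that regrading changes which events match the section 5.3 example. This has weight, because the summaries are the part that repairs the analysis. Without a grading rule, however, the severity table would still call every such event mild, beside a laboratory table that might show otherwise.

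**Conclusion.** The gap is real but modest. Followed exactly, the grading rule gives an uninformative severity result for every symptom-free laboratory AE, and no planned summary recovers the size. The loss lies in how safety is reported, not in whether events are detected, counted or acted on.

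The number of participants affected cannot be estimated, because the documents give no frequency of aminotransferase rises at 10 mg. A reader might also infer that the trial would report all hepatic AEs as mild. That would require every hepatic AE to be symptom-free, which nothing in the documents establishes.

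The conclusion assumes that Table 2 is applied as written. An investigator could grade a large rise higher by judgement, but the grade would then rest on no stated criterion. It also assumes that no grading rule sits in a document outside those supplied. The values in the illustration are invented to show scale.

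**What to change.** 1. **Section 9.3.** Add descriptive laboratory summaries for OCA versus placebo: change from Day 0, shift tables, and the maximum post-baseline ALT and AST as multiples of both the upper limit of normal and the Day 0 value. Include unscheduled results, and show how many participants contribute at each visit.
2. **Section 8, subheading 7.2 and Table 2.** Keep Table 2 for clinical AEs. Name a published numerical scale for laboratory AEs. Correct the pointer from Table 3 to Table 2.
3. **Section 5.3.** The clinical team must reconcile the grade 3 wording with the revised grading. No threshold or stopping rule is proposed here.

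The cost is one or two extra safety tables and some protocol and CRF wording. No new samples are needed, since the tests are already drawn at Day 0, Day 28 and Day 42. Some events will carry a higher grade than they would now, which is why item 3 has to accompany item 2.
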